4.6.2. Benefit Assessment

Data from earlier studies [Haldar, 2009; Nair, 2009; Pavord, 2012] attest to the clinical utility of mepolizumab in the treatment of severe eosinophilic asthma which was confirmed in the Phase III studies MEA115575 and MEA115588 [Bel, 2014; Ortega, 2014]. The safety syringe provides a more convenient mode of delivery from previous mepolizumab administration and potentially provides patients an option to self-administer mepolizumab at home.

4.6.3. Overall Benefit:Risk Conclusion

Current data from mepolizumab preclinical and clinical development indicate the ability of mepolizumab to inhibit IL-5 leading to consistent reduction in blood eosinophils, with demonstration of clinical benefit in the treatment of conditions associated with eosinophilic inflammation, such as asthma. Data from the Phase III asthma programme with mepolizumab demonstrates, compared to placebo, a reduction in asthma exacerbations, improvements in asthma control and quality of life (as measured by the ACQ and SGRQ, respectively), improvements in lung function and a reduction in oral corticosteroid use in those subjects on chronic OCS treatment. To date, the safety profile of mepolizumab has been favourable and the benefit/risk profile remains positive in patients with severe asthma. The change in drug product presentation from a lyophilised drug product to a liquid drug product in an safety syringe is not anticipated to alter the overall benefit:risk. The ability of subjects to self-administer treatment will be closely observed in the clinic and subjects will be instructed to seek medical attention if they experience any abnormal symptoms following administration at home, away from the clinic.

5. SELECTION OF STUDY POPULATION AND WITHDRAWAL CRITERIA

Specific information regarding warnings, precautions, contraindications, adverse events, and other pertinent information on the GSK investigational product or other study treatment that may impact subject eligibility is provided in the IB/IB supplement(s).

Deviations from inclusion and exclusion criteria are not allowed because they can potentially jeopardise the scientific integrity of the study, regulatory acceptability or subject safety. Therefore, adherence to the criteria as specified in the protocol is essential.

5.1. Inclusion Criteria

A subject will be eligible for inclusion in this study only if all of the following criteria apply:

AGE

1. **Age:** At least 12 years of age inclusive, at the time of signing the informed consent. [For those countries where local regulations permit enrolment of adults only, subject recruitment will be restricted to those who are ≥ 18 years of age]

TYPE OF SUBJECT AND DIAGNOSIS INCLUDING DISEASE SEVERITY

2. **Asthma:** A physician diagnosis of asthma for ≥ 2 years that meets the National Heart, Lung and Blood Institute guidelines [[National heart, lung and blood institute \(NIH\)](#), 2007] or Global Initiative for Asthma (GINA) guidelines [[GINA](#), 2015]

3. **Mepolizumab treatment:**

- a. Not receiving mepolizumab treatment at Visit 1
(NB: these subjects must also meet inclusion criteria 4, 5, 6 and 7).

OR

- b. Receiving 100 mg SC mepolizumab administered for the treatment of severe eosinophilic asthma every 4 weeks for at least 12 weeks prior to Visit 1.

The following inclusion criteria are only applicable to those subjects NOT receiving mepolizumab treatment at Visit 1:

4. **Eosinophilic asthma:** A high likelihood of eosinophilic asthma as per the required 'Continuation to Treatment' - Criterion 2.
5. **Inhaled Corticosteroid:** A well-documented requirement for regular treatment with high dose inhaled corticosteroid (ICS) in the 12 months prior to Visit 1 with or without maintenance oral corticosteroids (OCS).
 - For subjects ≥ 18 years old:
 - ICS dose must be ≥ 880 mcg/day fluticasone propionate (FP) (ex-actuator) or equivalent daily.
 - For ICS/long-acting-beta-2-agonist (LABA) combination preparations, the highest approved maintenance dose in the local country will meet this ICS criterion.
 - For subjects ≥ 12 to ≤ 17 years old:
 - ICS dose must be ≥ 440 $\mu\text{g/day}$ FP (ex-actuator) or equivalent daily.
 - For ICS/LABA combination preparations, the mid-strength approved maintenance dose in the local country will meet this ICS criterion.

6. **Controller Medication:** Current treatment with an additional controller medication, besides ICS, for at least 3 months or a documented failure in the past 12 months of an additional controller medication [e.g., long-acting beta-2-agonist (LABA), leukotriene receptor antagonist (LTRA), or theophylline] for at least 3 successive months.
7. **Exacerbation history:** Previously confirmed history of one or more exacerbations requiring treatment with systemic corticosteroid (CS) [intramuscular (IM), intravenous, or oral] in the 12 months prior to Visit 1, despite the use of high-dose ICS. For subjects receiving maintenance CS, the CS treatment for an exacerbation must have been a two-fold dose increase or greater.

WEIGHT

8. **Body weight:** A minimum ≥ 40 kg at Visit 1

SEX

9. **Gender:** Male or Female

Females:

A female subject is eligible to participate if she is not pregnant (as confirmed by a negative urine human chorionic gonadotrophin (hCG) test), planning to become pregnant during the time of study participation (and up to 16 weeks after the last dose), not lactating, and at least one of the following conditions applies:

- a. Non-reproductive potential defined as:
- Pre-menopausal females with one of the following:
 - Documented tubal ligation
 - Documented hysteroscopic tubal occlusion procedure with follow-up confirmation of bilateral tubal occlusion
 - Hysterectomy
 - Documented Bilateral Oophorectomy
 - Postmenopausal female (see [Appendix 3](#) for specific criteria).
- b. Reproductive potential and agrees to follow one of the options listed in the Modified List of Highly Effective Methods for Avoiding Pregnancy in Females of Reproductive Potential (FRP) (see [Appendix 3](#)) from 30 days prior to the first dose of study medication and until 16 weeks after the last dose of study medication and completion of the End of Study/Early Withdrawal visit.

The investigator is responsible for ensuring that subjects understand how to properly use these methods of contraception.

INFORMED CONSENT

10. **Informed Consent:** Capable of giving signed informed consent which includes compliance with the requirements and restrictions listed in the consent form and in this protocol.

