The study is single arm in which all subjects will receive mepolizumab 100 mg SC from the liquid drug product in safety syringe presentation. Each subject will participate in the study for up to 18 weeks and will have a Pre-screening visit (Visit 0), a Screening visit (Visit 1) and a 12-week Treatment Period (Visits 2 through 4) which concludes with End of Study assessments (Visit 5) 4 weeks after the last dose of mepolizumab at Visit 4.

Type and Number of Subjects

Male or female subjects aged 12 years or older with severe eosinophilic asthma. Subjects must either have been receiving mepolizumab administered SC for the treatment of severe eosinophilic asthma every 4 weeks for at least 12 weeks prior to Visit 1 or, if not previously using mepolizumab, must be using high dose inhaled corticosteroids plus an additional controller with a history of 1 or more exacerbations requiring systemic corticosteroids in the 12 months prior to Visit 1.

Approximately 75 subjects will be screened to achieve 55 enrolled subjects with the aim of achieving 50 completed/evaluable subjects.

Sample Size Calculations and Statistical Analyses

No formal sample size calculations were performed. Assuming a ~30% dropout rate during screening, approximately 75 subjects will be screened in order to enrol 55 subjects (attempting at least one self-administration of mepolizumab). Assuming a dropout rate of up to 10% during the study, 55 enrolled subjects should provide at least 50 subjects with complete study data.

The number and percentage of subjects successfully able to self-administer their doses will be presented together with 95% confidence intervals. No hypothesis testing will be performed.

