5.2. Exclusion Criteria

A subject will not be eligible for inclusion in this study if any of the following criteria apply:

CONCURRENT CONDITIONS/MEDICAL HISTORY (INCLUDES LIVER FUNCTION AND QTc INTERVAL)

1. **Concurrent Respiratory Disease:** Presence of a known pre-existing, clinically important lung condition other than asthma. This includes current infection, bronchiectasis, pulmonary fibrosis, bronchopulmonary aspergillosis, or diagnoses of emphysema or chronic bronchitis (chronic obstructive pulmonary disease other than asthma) or a history of lung cancer.
2. **Eosinophilic Diseases:** Subjects with other conditions that could lead to elevated eosinophils such as Hypereosinophilic Syndromes, including Churg-Strauss Syndrome, or Eosinophilic Esophagitis. Subjects with a known, pre-existing parasitic infestation within 6 months prior to Visit 1 are also to be excluded.
3. **Malignancy:** A current malignancy or previous history of cancer in remission for less than 12 months prior to screening (Subjects that had localized carcinoma of the skin which was resected for cure will not be excluded).
4. **Immunodeficiency:** A known immunodeficiency (e.g. human immunodeficiency virus – HIV), other than that explained by the use of corticosteroids taken as therapy for asthma.
5. **Other Concurrent Medical Conditions:** Subjects who have known, pre-existing, clinically significant cardiovascular, endocrine, autoimmune, metabolic, neurological, renal, gastrointestinal, hepatic, haematological or any other system abnormalities that are uncontrolled with standard treatment.
6. **Liver Disease:** Known, pre-existing, unstable liver disease (as defined by the presence of ascites, encephalopathy, coagulopathy, hypoalbuminaemia, esophageal or gastric varices or persistent jaundice), cirrhosis, and known biliary abnormalities (with the exception of Gilbert's syndrome or asymptomatic gallstones).
7. **ECG Assessment:** QT interval corrected for heart rate by either Fridericia's or Bazett's formula $QTc(F)/QTc(B) \geq 450\text{msec}$ or $QTc(F)/QTc(B) \geq 480\text{ msec}$ for subjects with Bundle Branch Block at Visit 1.

CONCOMITANT MEDICATIONS

8. **Xolair:** Subjects who have received omalizumab within 130 days of Visit 1.
9. **Other Monoclonal Antibodies not including mepolizumab:** Subjects who have received any monoclonal antibody (other than Xolair) to treat inflammatory disease within 5 half-lives of Visit 1.

- | |
|--|

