| 
10. Investigational Medications: Subjects who have received treatment with an investigational drug, other than mepolizumab within the past 30 days or five terminal phase half-lives of the drug whichever is longer, prior to visit 1 (this also includes investigational formulations of marketed products) or experimental anti-inflammatory drugs (non biologicals) in the past 3 months.
 
11. Chemotherapy: Subjects who have received chemotherapy within 12 months prior to Visit 1.
 |
|--|

RELEVANT HABITS

- | |
|---|
| 
12. Alcohol/Substance Abuse: A history (or suspected history) of alcohol misuse or substance abuse within 2 years prior to Visit 1.
 |
|---|

CONTRAINDICATIONS

- | |
|---|
| 
13. Hypersensitivity: Subjects with hypersensitivity to mepolizumab or to any of the excipients (sodium phosphate, citric acid, sucrose, EDTA, polysorbate 80).
 |
|---|

DIAGNOSTIC ASSESSMENTS AND OTHER CRITERIA

- | |
|--|
| 
14. Adherence: Subjects who have known evidence of lack of adherence to controller medications and/or ability to follow physician's recommendations.
 |
|--|

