6.11.2. Prohibited Medications and Non-Drug Therapies

The following medications ([Table 2](#)) are not allowed prior to screening (Visit 1) according to the following schedule, or during the study:

Table 2 Medications not allowed prior to the Screening Visit 1 and throughout the study

Medication	Washout Time Prior to Screening Visit 1
Omalizumab (Xolair)	Within 130 days
Other monoclonal antibodies (other than Xolair or mepolizumab) to treat inflammatory disease	5 half-lives
Investigational drugs (excluding mepolizumab)	30 days or 5 half-lives whichever is longer
Chemotherapy	12 months

Recreational drug use is not allowed during the study.

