7.2.1. Critical procedures performed at Screening (Visit 1)

- Medical history including smoking status, history of sinusitis, nasal polyposis, aspirin sensitivity, current treatment, duration of asthma, courses of rescue corticosteroids in the past 12 months, history of previous intubations, asthma exacerbation history in the previous 12 months, asthma triggers and smoking history
- Prior experience of needle use including any history of self-administration using an safety syringe device
- Therapy history, including use of mepolizumab, omalizumab or previous biologics in the past 12 months (see Section 6.11.2). For subjects currently receiving mepolizumab, data will be collected on whether mepolizumab treatment was initiated based on an eosinophil count within 6 weeks of starting treatment or a historical measurement collected in the 12 months prior to initiating mepolizumab. The blood eosinophil count closest to the initiation of mepolizumab treatment, if available, should be recorded.
- Cardiovascular medical history/risk factors (as detailed in the eCRF). This assessment must include a review of the subject responses to the cardiovascular assessment questions and height, weight, blood pressure, smoking history, medical conditions, and family history of premature cardiovascular disease
- Physical exam (see Section 7.7.4)
- Vital signs (see Section 7.7.5)
- Resting 12-lead ECG (see Section 7.7.6)
- Laboratory tests (see Section 7.7.7). This should include:
 - Chemistry
 - Haematology with differential count
 - Urinalysis
 - Urine pregnancy test- for all women of child bearing potential

- Follicle stimulating hormone (FSH) will be assessed to confirm child-bearing status (if applicable)
- Parasitic screening (only in countries with a high-risk or in subjects who have visited a high-risk country)
- Review of Inclusion/Exclusion criteria
- Review of exacerbations, SAEs

Procedures conducted as part of the subject's routine clinical management [e.g. blood eosinophil counts] and obtained prior to signing of informed consent may be utilised for Screening or baseline purposes provided the procedure meets the protocol-defined criteria and has been performed within the timeframe defined in the Time and Events Schedule.

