5.4.2. Sub-group Display Descriptors

Data Displays for Reporting		
Subgroup Descriptor	Category	Order
Baseline Mepolizumab Use	No	1
	Yes	2
Injection Site	Abdomen	1
	Upper Arm	2
	Thigh	3

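### The 'No' level of baseline mepolizumab use rests on Visit 1 status alone, so the plan permits recent stoppers to be summarised together with untreated subjects

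*Protocol*

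**What the plan says.** **Entry routes.** Protocol Section 5.1, criterion 3, offers two. Route 3a is "Not receiving mepolizumab treatment at Visit 1". Route 3b is 100 mg SC "every 4 weeks for at least 12 weeks prior to Visit 1". Route 3a subjects must also meet criteria 4 to 7 (eosinophilic phenotype, high-dose ICS, a second controller, exacerbation history). None of these mentions earlier mepolizumab.

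**Washouts.** Exclusion 9 is headed "Other Monoclonal Antibodies not including mepolizumab", exclusion 10 covers "Subjects who have received treatment with an investigational drug, other than mepolizumab within the past 30 days", and the matching row of Table 2 in Section 6.11.2 reads "Other monoclonal antibodies (other than Xolair or mepolizumab) to treat inflammatory disease". No rule sets a mepolizumab-free interval.

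**Descriptions of the group.** The synopsis writes "if not previously using mepolizumab", and Section 6.11.1 likewise speaks of subjects without earlier mepolizumab. Section 4.4 refers to status at study entry, but it interprets the group's results as pre-steady-state and supports this with data from previously untreated subjects in another trial.

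**The analysis split.** Protocol Sections 9.4.3 and 9.4.4 call the split previous use but define it by status at Visit 1. SAP Section 5.4.2 lists "Baseline Mepolizumab Use" with the levels No and Yes, and mock shell TAB_POP4 asks about current treatment. The split is applied to PK (SAP 8.1), eosinophils (SAP 9.1) and both antibody assays (SAP 12.1).

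**Data already collected.** Section 7.2.1 requires "Therapy history, including use of mepolizumab, omalizumab or previous biologics in the past 12 months". Section 6.11.1 requires names and administration dates of asthma medication for the same 12 months.

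**The concern.** The label and the interpretation suggest an untreated group, but the definition does not secure one. A subject who has recently stopped mepolizumab may still have drug in the blood and a suppressed eosinophil count at Visit 2. The SAP takes the last value before the Visit 2 dose as baseline (Section 14.3.1.1). For such a subject the ratio to baseline would lie nearer 1 than in an untreated subject, and the Week 4 trough would include residual drug. Earlier exposure also complicates the reading of an antibody result.

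The 'No' group is where the eosinophil effect of the new presentation can be seen, because current users start from a treated baseline. Section 4.4 also intends its troughs to be set against historical data. Baseline use is the only subgroup applied across all three domains (PK, eosinophils and antibodies).

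**Working it through.** The plan states no figure on this point, so there is none to reproduce. The check has three steps.

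**1. Can a recent stopper enter as 'No'?**
- Route 3a: met once treatment has stopped before Visit 1. A subject with under 12 weeks of mepolizumab fails 3b but could enter by 3a after stopping.
- Washouts: none covers mepolizumab.
- Eosinophil criterion (Section 5.3): either at least 300 cells/µL at some time in the 12 months before Visit 1, or at least 150 cells/µL at Visit 1. The second would tend to screen out a suppressed subject. The first can be met by a count taken before a recent course.
- Analysis: no planned display separates former users from untreated subjects.

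So the route is open, though narrow.

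**2. Size for the eosinophil ratio (illustration).** Let r be the true geometric mean ratio in untreated subjects, s the ratio in stoppers and c the stopper share. The documents give none of these. The pooled ratio is r^(1−c) × s^c. With s = 1.0 (no recovery before Visit 2, the worst case), reported/true = r^(−c):

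| r | c = 5% | c = 10% |
|---|---|---|
| 0.15 | 1.100 | 1.209 |
| 0.20 | 1.084 | 1.175 |
| 0.30 | 1.062 | 1.128 |

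The ratio is therefore 6-10% too high at 5% and 13-21% too high at 10%. On the reduction scale, with r = 0.25 and c = 10%, 0.25 becomes 0.25^0.9 = 0.287, so a 75% reduction is reported as 71%.

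**3. Size for the Week 4 trough of one stopper (illustration).** Assume a one-compartment model without an absorption phase, earlier steady state on the same 4-weekly dose, and a half-life h of 14 to 28 days (assumed). Write q = 2^(−28/h). In units of the concentration from one dose, the former steady-state trough is q/(1−q). With g days from last dose to Week 0, the fraction of that trough remaining at Week 0 is 2^(−(g−28)/h), and Week 4 trough relative to an untreated subject = 1 + [q/(1−q)] × 2^(−(g−28)/h).

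| Gap to Week 0 | Fraction of old trough left (h = 14 to 28) | Week 4 trough relative to untreated |
|---|---|---|
| 6 weeks | 0.50 to 0.71 | 1.17 to 1.71 |
| 9 weeks | 0.18 to 0.42 | 1.06 to 1.42 |
| 12 weeks | 0.06 to 0.25 | 1.02 to 1.25 |

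Example at 6 weeks, h = 14: q = 0.25, q/(1−q) = 0.333, fraction 0.50, giving 1 + 0.167 = 1.17. These are effects in one subject; the effect on the group mean shrinks with the stopper share.

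**The case against.** The case for leaving the plan alone is substantial.

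- **A reader might infer that recent stoppers are in fact pooled.** The documents do not support that. They leave the door open and show nobody passing through it. A suppressed stopper using the historical count would generally have started and stopped within the same 12 months, and also needs high-dose ICS and an exacerbation in that year. Screening adds 1 to 4 weeks. This objection stands.
- **A reader might take the washout exemptions as intent to admit recent stoppers.** They are needed because route 3b enrols current users. They show only that no other rule closes the gap.
- **A reader might call baseline use the only stratifier.** It is not: injection site is also used for PK and eosinophils.
- **Carry-over would be partly visible.** Pre-dose Week 0 concentrations are listed, plotted by subject and summarised by baseline use. The eosinophil shells show Screening and Week 0 values with minima, and the ratio tables give medians, which a few subjects barely move. This stands in part. Concentrations can be traced to a subject, but the planned eosinophil displays are summaries only, and nothing links either to treatment history.
- **The shift is small against the noise.** Assume 25 'No' subjects and a log SD of 0.6 to 1.0. The upper 95% limit then lies above the estimate by a factor of exp(2.064 × 0.6/5) = 1.28 to exp(2.064 × 1.0/5) = 1.51, more than the 6-21% worst case. At 5-10%, one to three people are involved. This is fair, though a shift in a known direction differs from sampling error.
- **No decision hangs on it.** The primary and secondary endpoints do not use the subgroup, no hypothesis is tested, and PK comparability is assigned to Study 204958.

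**Conclusion.** The point holds as a minor one. The 'No' level is defined by Visit 1 status with no interval since last dose, while other parts of the protocol describe or interpret the same group as not previously treated. The plan therefore permits recent stoppers to be pooled with untreated subjects.

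The 6-10% (5% stoppers) and 13-21% (10% stoppers) figures for the eosinophil ratio are upper bounds for those shares. They rest on an assumed untreated ratio of 0.15-0.30 and on complete suppression at baseline in stoppers; any recovery before Visit 2 makes them smaller. The consequence is confined to descriptive PK, eosinophil and antibody displays. The case for acting is that the data are already collected and the remedy is cheap, not that the bias is likely to be large.

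**What to change.** Keep the protocol-defined No/Yes split and leave eligibility alone.

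1. In SAP Section 5.4.2, add a derived flag for any mepolizumab in the 12 months before Visit 1, with time since last dose, from the therapy history and medication dates already collected. Check it against the Visit 2 pre-dose concentration.
2. If any 'No' subject is flagged, repeat the 'No' rows of the PK, eosinophil and antibody summaries without them (Tables 8.2, 9.3, 9.4, 12.2 and 12.5), and identify them in the listings. A separate summary line for so few people would tell the reader little.
3. Record the addition in SAP Section 2.1, which now declares no change beyond an extra population.
4. Reconcile the synopsis and Section 6.11.1 with criterion 3a, so that the group is described in one way.

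The cost is one derived variable and, only if someone is flagged, a few extra displays. A 12-month look-back cannot establish that a subject was never treated. This limit matters mainly for antibodies and should be stated in a footnote. Redefining 'No' as never treated is not recommended: it would depart from Protocol Sections 9.4.3 and 9.4.4 and could not be verified from the 12-month history.
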